1 STUDY INFORMATION

1.1 Full/Long Title of the Study

Real world testing of an artificial intelligence-enabled app as an early intervention and support tool in the mental health referral care pathway

1.2 Short Study Title / Acronym

Clinical investigation of **Wysa**

1.3 Protocol Version Number(s) and Date(s)

0.1	Initial draft	25 October 2021
0.2	Circulation drafts	05 November 2021
0.3	Revisions following investigator review	26 November 2021
0.4	Minor revisions	01 December 2021
0.5	UoP Sponsor Review	02 December 2021
0.6	Minor drafting amendments	12 January 2022
0.7	Drafting amendments	7 February 2022
0.8	Amendments following Sponsor/faculty review	21 February 2022
0.9	Faculty approved version for HRA/REC review	19 March 2022
1.0	Amendments following REC Provisional Opinion	22 May 2022
1.1	Minor amendments following MHRA review	29 September 2022

1.4 Research Reference Numbers

IRAS Number:	310377
SPONSORS Number:	AM1000411, 3173
NIHR Award Number:	AI_AWARD02176

4 ABBREVIATIONS AND KEY TERMS

Table 2. Abbreviations

Abbreviation / Key Term	Full Phrase / Definition
A&E	Accident and Emergency (Emergency department)
AI	Artificial Intelligence
API	Application Programming Interface
CEO	Chief Executive Officer
CNWL	Central North West London (NHS Foundation Trust)
CONSORT	Consolidated Standards of Reporting Trials
DPA 2018	Data Protection Act 2018
EBCD workshops	Experience-based co-design workshops
EC	European Commission
EQ-5D-5L	EuroQoL 5 Dimensions
FREIC	Faculty Research Ethics and Integrity Committees
GAD-7	General Anxiety Disorder questionnaire
GDPR	General Data Protection Regulation
GP	General Practitioner
HRA	Health Research Authority
IAPT	Improving Access to Psychological Therapies
ICMJE	International Committee of Medical Journal Editors
ICO	Information Commissioner's Office
IRAS	Integrated Research Application System
MeSH	Medical Subject Headings
NASSS	Non-adoption, Abandonment, Scale-up, Spread, and Sustainability framework
NHS	National Health Service
NIHR	National Institute for Health Research
PERC	Patient Experience Research Centre
PHQ-9	Patient Health Questionnaire

PPI	Patient and Public Involvement
RCT	Randomised controlled trial
REC	Research Ethics Committee
SF-12	Short Form 12 health survey
SPIRIT-AI	Standard Protocol Items: Recommendations for Interventional Trials - Artificial Intelligence
SW AHSN	South West Academic Health Science Network
SWIFT	Structured What-IF Technique (prospective hazards analysis method)
TFA	Theoretical Framework of Acceptability
Wysa	Wysa Limited (Company Number: 11220172)

5 STUDY SUMMARY

Table 3. Study Summary

Study Title	Real world testing of an artificial intelligence-enabled app as an early intervention and support tool in the mental health referral care pathway
Short title	Clinical investigation of Wysa
Study Design	The study proposed is a non-blinded randomised controlled trial and mixed-methods evaluation to inform the impact of Wysa on depression and/or anxiety symptoms and user engagement and perceptions.
Study Participants	The target population of the will include individuals over the age of 18 years who are referred, or self-refer, to Improving Access to Psychological Therapies programme (IAPT) for mental health support.
Planned Size of Sample	The planned sample size is 480 individuals from the three provider sites of the London Community Living Well Service (run by the CNWL NHS Foundation Trust).
Follow up duration	The study implementation and follow-up period will last for nine months, with the primary outcome being measured at three months post-randomisation.
Planned Study Period	The study will last 17 months which includes five months of evaluation refinement, ethical approval, technical integration and testing, A further nine months of implementation and follow-up, ending with three months of post-evaluation analysis and preparation for dissemination.
Research Question/Aim(s)	
The study aim is to establish real-world evidence of the Wysa impact on mental health outcomes (depression and/or anxiety symptoms) in individuals waiting for treatment through the NHS standard mental health care pathway.
 
The main research question of the study is: how does an Artificial Intelligence (AI)-enabled self-help and triage app impact the mental well-being of patients who have been referred to the IAPT service for mental health support?

5.2 Role of Study Sponsor and Funder

This study is funded by an NIHR Artificial Intelligence in Health and Care Award granted to Wysa. Wysa distributes on behalf of NIHR funding to the University of Plymouth, the Institute of Cancer Research, and [name] for this study execution. This funding arrangement is governed by a collaboration agreement which defines the University of Plymouth as being responsible for the study design, conduct, data analysis and interpretation, manuscript writing, and dissemination of results in collaboration with the academic collaboration including the Institute of Cancer Research. Whilst Wysa has contributed and reviewed the study design and will support the trial in providing technology support, the academic collaboration, led by the University of Plymouth, is solely responsible for the study execution and dissemination of results to assure an independent assessment of Wysa technology. The academic collaboration maintains a free and independent unrestricted right of publication of the study's findings as to avoid any conflict of interest.

5.3 Roles and Responsibilities of Study Management Committees/Groups and Individuals

A study steering board composed of the Chief Investigator, Principal Investigators, Co-Investigators, a member of the public, Wysa's CEO and Clinical Lead, and an external researcher (from the study) will meet every two months to review progress against the protocol to provide study governance and oversight. Reports shall be distributed for review by the study team for action. An independent Data Governance Advisory Board will be formed to help further steer the project.

Wysa will appoint a Patient and Public Involvement (PPI) committee. With input from the Imperial College Patient Experience Research Centre (PERC) and the South West Academic Health Science Network (SW AHSN) and based on NIHR Involve guidance, a term of reference, confidentiality agreement and a background assessment form to Wysa to structure the aims of the PPI group. Membership of this Wysa PPI group is voluntary but requires members to be committed to attend meetings and to respond to emails/ correspondence. The initial term of membership is for the duration of the study from early in the preparation phase (app. Dec 2021 / Jan 2022). Further details about PPI are included in the study protocol (see section 9.4).

5.5 Keywords

Artificial Intelligence (MeSH), Mental Health (MeSH), Telemedicine (MeSH)

6 STUDY FLOW CHART

This project will conduct a real-world evaluation of Wysa as an early intervention tool introduced into the mental health referral pathway for adult IAPT service. There is currently an average wait time for IAPT between referral and treatment start of 8+ weeks with 95% of people starting treatment within 18 weeks [1]. Wysa will be made available to patients upon referral to IAPT. The control group will continue with service as usual whilst the test group will interact with Wysa while waiting for treatment.

Wysa will remain available to patients throughout their progression through the standard clinical pathway. Patients will be provided with information about the study at their initial referral point and will be contacted by our research assistants to collect informed consent and provide the product link. This will enable Wysa to offer immediate support tools and monitoring. While patients are waiting for treatment, Wysa will serve as a screening support tool for flagging assessment needs to the clinical team. After patients have received treatment, Wysa can be used as an extended monitoring tool. This is in line with the IAPT manual 2018's future goal [2] of using an app to prompt patients to fill in key outcome measures at regular intervals during the follow-up year, providing patients with easy access to their relapse prevention plan, alerting the service if relapse has occurred, and facilitating the scheduling of booster sessions. Figure 1 demonstrates the current clinical IAPT pathway with the proposed study procedures in blue.

[figure not shown]

Figure 1. Current clinical pathway for adult IAPT referral and proposed study procedures (blue) (adapted from [2])

Based on the artificial intelligence (AI) recommendations generated by Wysa, patients may be passed to the IAPT for a full assessment using a combination of outcome measure scores and language used within the tool. A copy of the patients' responses to outcome measures will be

automatically pushed into their electronic patient record through the Mayden clinical information system and an automated email will be sent to the referrals coordinator to flag the need for onward referral.

Wysa will have two pathways to crisis alert and response. The first pathway is for patients to trigger the crisis response pathway by pressing a manual override button on the app. The second pathway is for the app to trigger the crisis response because of an individual's response to an outcome measure or the language used in free conversation with the AI. Because this pathway can be triggered by the app's natural language processing, the AI regularly checks in with the patient to ensure they are understanding them correctly.

When Wysa or the user triggers the crisis response pathway, users will be provided with a stepped crisis plan including grounding exercises, local crisis helplines, or a recommendation to attend A&E where there is significant injury or risk to life. Data will be collected indicating the number of false positives identified by the AI. Coinciding with this, the app pushes an update to the patient's linked electronic patient record through Mayden and sends an alert email to the 'Clinician of the Day' at each trust for human follow up.

[figure not shown]

Figure 2. High-level study Gantt chart

7 INTRODUCTION

7.1 Background

Mental health concerns can have significant negative impacts on health, well-being, and economies [3]. There is a growing recognition of the importance of mental health, which is reflected across the UK and international health sectors. Mental health concerns are projected to be the global leading cause of mortality and morbidity by 2030 [4]. Globally, depression and anxiety are estimated to cost US\$1 trillion each year [5]. However, the impact of mental health conditions is not limited to those who have official diagnoses. It is estimated that 1-in-6 people will have experienced a common mental health concern in the past week below the threshold of a diagnosable mental health concern [6].

Mental health conditions can have wide ranging negative impacts on individuals' lives and well-being. For instance, depression and anxiety disorders can lead to a range of adverse psychological, social, and employment outcomes [7]. Mental health conditions also affect physical health; anxiety, depression, and substance abuse disorders have been associated with an increased risk of non-communicable diseases such as diabetes, cancer, and cardiovascular diseases [8–10]. Prolonged and severe mental illness is associated with reduced life expectancy; with people at risk of dying an average of 15 years sooner than those without severe mental illness. The cause of death in such cases is often avoidable, with two thirds of the deaths caused by heart disease and cancer, often because of excess smoking [11].

Common mental health concerns frequently go unsupported; an estimated 75% of people who would benefit from support for common mental health concerns do not receive it, resulting in approximately costs of £105.2 billion a year to the UK economy [12,13]. Lack of support at an early stage can lead to poorer physical health outcomes and the development of unhealthy coping strategies such as alcohol consumption or poorer diet choices [14]. Of those people with recognised mental health conditions, negative experiences with mental health services are commonly reported [15,16]. Nearly half of survey respondents (44%) who had received NHS therapies in 2019 reported that they had to wait too long to access them [15,16] and in 2017, half of the respondents reported only being offered pharmaceutical treatment [17]. Long wait times to access mental health services can have significant health and economic impacts; a recent study by the Royal College of Psychiatrists found that 38% of people waiting for treatment reach out to crisis services and 11% go to A&E [18].

The economic cost of mental health conditions can occur from sick days, reduced quality of life, and reduction in productivity [3,4]. Depression, anxiety, or stress are some of the most common reasons for lost workdays [19]. Symptoms of common mental health conditions like depression and anxiety have increased since before the Covid-19 pandemic, referrals to mental health services decreased, and the number of people presenting in crisis increased [20]. It is estimated that the economic cost for the UK due to poor mental health is greater than NHS spending on mental health services [21]. Reducing the impact of common mental illness will increase our national income and productivity.

In 2008, a programme for IAPT was launched by the NHS [22]. The number of referrals demonstrates the demand for mental health services in the UK; over 1.5 million referrals to adult IAPT services were made in 2018/2019 [23]. Over a quarter of these patients (n=441,775) were discharged without face-to-face contact following a telephone referral and another quarter (n=440,344) were discharged with a workbook [23]. With each contact costing an average of approximately £100 [24],

the total cost to the NHS was over £90 million. This figure does not include additional care needs or A&E attendances for those individuals who were unable to wait up to 12 weeks for assessment.

The NHS Long Term Plan aims to promote digitally enabled care, improve access to mental health support for 1.9 million people, and support NHS Trusts at meeting their referral waitlist key performance indicators (KPIs) [25]. Wysa's solution is well-placed to support these goals by providing a digital early intervention approach that can be implemented at the point of self-referral, reducing the need for inappropriate assessments and escalating cases based on clinical outcome measures as needed. This is also aligned with NHSx's missions, particularly the aims to use digital technology to improve health and care productivity and empower people to access information and services to manage their own health [26], and the Industrial Strategy's grand challenge of embedding AI to improve productivity in the UK [27].

7.2 Rationale

A key issue with the current mental health service provision is lack of accessibility. Our solution enables immediate service provision at the point of referral, to mitigate the impact of long wait times to access mental health services. Onboarding processes at the point of referral to IAPT involve collecting routine outcome measures (aligned to existing service referral measures). Users are asked to provide information and goals to personalise the guided self-help or escalation recommendations. These are provided using a combination of AI-enabled self help tools, natural language processing and conversation engines. Our Application Programming Interface (API) through the Mayden Prism system then pushes data directly into the iaptus electronic patient records and automates safety alerts.

Our preliminary work suggests that implementing Wysa's self help tools at the onboarding stage will result in improved outcomes for the service user, whilst automations in the referral process will result in less assessments that are then screened out of the service and a more comprehensive risk identification whilst awaiting assessment [28]. This is based upon our previous findings from our 2018 study showing a significant decrease in depressive symptoms in users of Wysa versus non users [28].

7.2.1 Benefits for patients and public

IAPT services used a stepped care model, with Steps 2-4 reflecting increasing intervention beyond the GP level; Step 2 is conducted by psychological wellbeing practitioners to manage mild to moderate mental health conditions, while Steps 3 and 4 involve CBT therapists and other specialised treatments for more severe or complex conditions [29]. Whilst computerised Cognitive Behavioural Therapy and guided self-help are recognised treatment options for step two low intensity support in IAPT, they are often offered later in the referral pathway resulting in a higher assessment cost and poorer user experience. The use of Wysa could help to improve patient experience of, and outcomes from, their use of mental health services, for example, by reducing their wait time to access evidence-based advice. Delivering timely and convenient evidence-based support could empower users to make choices about their health and coping strategies. The use of standard outcome measures also enables the app to escalate those patients in need of step three or higher intensity interventions. This solution also has the potential to reduce inequalities in service provision (e.g., those who might otherwise remain untreated [30] and is especially important for individuals from high risk groups (such as LGBTQ+ or Black and minority ethnic groups) who are least likely to receive support [31,32]).

7.2.2 Benefits for NHS and service provision

Wysa has the potential to benefit service provision by providing a more efficient care pathway. By providing mental health support and user outcome measures at the point of referral, rather than when patients are assessed and offered treatment, Wysa can help to identify users who have a more urgent need for treatment and escalate their care. Some users might find that Wysa sufficiently meets their needs for mental health support, which would reduce the number of patients who need to be assessed and treated in the standard care pathway and reduce the waiting times for patients who do need further care. Timely support provision and early identification of deteriorating mental health could enable earlier interventions before the patient's condition becomes more costly to their well-being and to the healthcare system.

7.3.3 Benefits for environment

Implementing automated support at an early intervention stage has the potential to reduce the number of face-to-face assessments both at the point of referral to the IAPT pathway and at the point of full assessment. This reduction could potentially contribute to a reduction in the demand for travel to attend appointments whilst also reducing the demand of building spaces, contributing to the NHS's Net Zero Carbon goal [33]. Early interventions also have the potential to prevent further ill health, which increases operational efficiency and reduces emissions [33]. If Wysa is proven effective and widely adopted, its early provision of self-help resources could help to prevent worsening mental health and identify people most at risk so that they can be treated before reaching a crisis. Evidence will be gathered as part of this project's health economic assessment to examine this hypothesis.

7.3 Theoretical Frameworks

Two frameworks will form the theoretical basis for the study:

1. Long-term adoption and suitability to further trials will be evaluated using the Non-Adoption, Abandonment and Challenges to the Scale-up, Spread and Suitability (NASSS) framework [34]. This framework is important to include because interventions can only add value if they are successfully adopted and used. This framework emphasises the consideration of the multiple levels - individuals and systems - that influence adoption and non-adoption.
2. The Theoretical Framework of Acceptability (TFA) will be used to structure the semi-structured interview guide [35]. This framework was chosen because it was developed specifically for health interventions, captures a multi-faceted view of acceptability (with seven components), and emphasises the importance of considering different time points when evaluating acceptability.

7.4 Research Question

The main research question of the study is: how does an AI-enabled self-help and triage app impact the mental well-being of patients who have been referred to the IAPT service for mental health support?

7.5 Aims and Objectives

The primary aim of this project is to establish real-world efficacy that patient use of Wysa while waiting for treatment through the NHS mental health care pathway positively impacts well-being by comparing system users with standard services users.

The secondary aims of this project are:

1. To examine the feasibility of using Wysa to identify users at high risk of a mental health crisis and escalate them to further care;
2. To examine levels of user engagement with Wysa;
3. To evaluate patient acceptability of an autonomous early intervention supporting mental health services;
4. To complete a full health economic assessment of using Wysa for autonomous early intervention and triaging support;
5. To assess the potential for sustainable adoption of Wysa in mental healthcare pathways.

[figure not shown]

Figure 3. Wisconsin logic diagram

8 METHODS

8.1 Trial Design

This study will use an efficacy non-blinded randomised controlled trial (RCT) and mixed methods (process evaluation) design. Quantitative methods will be used to evaluate Wysa's efficacy at improving mental health outcomes as well as to examine engagement. Quantitative and qualitative methods, specifically semi-structured interviews, will also be used to gather a more in-depth understanding of users' engagement with Wysa and their feedback regarding its acceptability (see Figure 4 for an overview).

[figure not shown]

Figure 4. Participant flow diagram

8.1.1 Timeline

The study will last 17 months: 5 months of evaluation refinement and technical integration and testing, 9 months of implementation and follow-up, and 3 months of post-evaluation analysis and preparation for dissemination.

8.2 Study Context

8.2.1 Participants

The target population of the study will include adult patients who are referred, or self-refer, to IAPT for mental health support.

8.2.2 Setting

Participants will be recruited from the Central North West London NHS Foundation Trust but the intervention (Wysa) is accessible to users through a mobile app available on Apple and Android smartphones.

8.2.3 Intervention(s)

Wysa is a guided self-help and triaging tool delivered to patients via an app or widget. It uses Natural Language Processing to understand individuals' written inputs but not to generate responses. Wysa makes use of a wide range of clinically underpinned modules whilst gamification, clinical outcome measures and AI promotes engagement, improving efficacy and triage and reducing the cost of scale.

Wysa is delivered as a standalone system which patients download directly onto their personal device. Upon self-referral or professional referral to IAPT services the individual is automatically sent

a download link via sms or email. Once downloaded, data from within the app, including outcome measures, tools used and crisis alerts are automatically pushed to the electronic patient record iaptus using the Mayden Prism software. When considering the application of AI to mental wellbeing, the ability to feel listened to is the most influential factor in patient satisfaction and response. Users need to feel able to share their thoughts with the AI and our user testimonials show that the anonymous nature of this text-based interaction is imperative to them, even though they know they are communicating with an AI. Wysa has benefited from over 6 million conversations around the world to build up a complex listening algorithm, rules engine and content library. Clinical safety is applied to our rules engine and Content library to ensure that we regularly test for appropriateness, empathy, and presence of triggers in cases of misdirection. Each of Wysa's AI models is validated on at least 10,000 records that are manually tagged and not a part of the training set. Overall, Wysa has 100 million conversations to draw upon, with over 2 million users globally, which helps us overcome the cold-start problem that most AI faces.

Wysa can be used as a native app through android or IOS or as a web widget.

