8.2.5 Outcomes

8.2.5.1 Primary Outcomes

The primary analysis will be the comparison of depression severity between users of the app and patients in the standard clinical pathway (see Table 5). The primary outcome will be measured at baseline and three months post randomisation. In line with the national recommendations laid out by the IAPT Manual, we will be using Wysa's AI automation to encourage users to complete the Patient Health Questionnaire (PHQ-9 [36]) and General Anxiety Disorder (GAD-7 [37]) routine outcome measures [2]. Depression severity was chosen as the primary outcome because the PHQ-9, a depression symptom measure, is recommended for use in all patients presenting to IAPT services [2].

Table 5. Primary Outcome Measurement

Primary Outcome	Outcome Measure
Depression severity	
Score on the PHQ-9 [36]

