8.4.1.2 Allocation Concealment Mechanism

Consenting participants will be inputted into a masked computer randomisation algorithm and the outcome will be recorded in an electronic record to conceal treatment allocation from study researchers. Participants will be sent an automatic email to inform them of their group assignment, and participants in the intervention group will receive the link to download Wysa.

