13.4 Appendix 4. GP Letter

[header: GP letter Participant Consented, v1.0, XX/XX/XXXX; study logo]

[GP Name]

[GP Practice]

[Address]

[Date]

[Study Address]

[Address]

[Telephone/Email/Social media]

Our ref: XXXX

Dear Dr [GP name]

Re: [participant's full name], [participant's date of birth], [participant's address]

We would like to inform you that [participant's full name] has consented to join the Wysa Study. This project is a collaboration between the University of Plymouth, the Institute for Cancer Research, Wysa Ltd, and the Central North West London NHS Foundation Trust. The project is funded by the NIHR AI in Health and Care Award (ref: AI_AWARD02176) and has full ethical approval from [Research Ethics Committee (ref: TBD)]. No action is needed on your part, but [participant's full name] has provided permission that should anything of concern arise as a result of their participation in our study, we will discuss this with you.

Our study aims to measure and characterise the impact of engaging with Wysa while waiting for their first appointment through the IAPT service on symptoms of depression and anxiety. Participants randomised into the intervention group will be invited to use the app while waiting for treatment; participants randomised into the control group will be given access to the app after 3 months.

Participation is voluntary – [participant's name] is free to withdraw from our study at any point. If you would like any further information or if there is anything you would like to discuss, then please do not hesitate to contact us.

Yours sincerely,

[CI's/PI's name] Team Member's name]

13.5 Appendix 5. SPIRIT-AI Checklist: Recommended items to address in a protocol and related documents for clinical trials evaluating AI interventions

Section		SPIRIT 2013 Item ^a	SPIRIT-AI Item		Section No
Administrative Information					
Title	1	Descriptive title identifying the study design, population, interventions, and, if applicable, trial acronym	SPIRIT-AI 1(i) Elaboration	Indicate that the intervention involves artificial intelligence / machine learning and specify the type of model.	1
			SPIRIT-AI 1(ii) Elaboration	Specify the intended use of the AI intervention.	1

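### Section 8.2.3 sends the Wysa link to everyone at referral, contradicting the intervention-only rule in 8.4.1.2, and the readable text does not order control access against the 3-month PHQ-9

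*Protocol*

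**What the plan says.** **Who gets the link, when and from whom**

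- Protocol 8.2.3 (Intervention(s)): "Upon self-referral or professional referral to IAPT services the individual is automatically sent" "a download link via sms or email". Consent, randomisation and arm are not mentioned.
- Protocol section 6 (Study Flow Chart): "Wysa will be made available to patients upon referral to IAPT". Patients "will be contacted by our research assistants to collect informed consent and provide the product link". That sentence names no arm, but the same section also says: "The control group will continue with service as usual whilst the test group will interact with Wysa while waiting for treatment".
- Protocol 8.4.1.2 (Allocation Concealment Mechanism): an automatic email tells participants their group, and "participants in the intervention group will receive the link to download Wysa". The SAP repeats this under its allocation concealment heading.

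**When controls get access**

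- Protocol 8.3.3.1 gives controls access once the control period is over, but does not define that period.
- The GP letter (Appendix 4) says "participants randomised into the control group will be given access to the app after 3 months".
- Protocol 8.2.5.1: "The primary outcome will be measured at baseline and three months post randomisation". Section 8.4.3.1 gives the same two time points and has controls answer by Qualtrics survey.

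None of the readable text makes control access depend on completing the 3-month PHQ-9, gives a window for that PHQ-9, or says which comes first.

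**The concern.** The three delivery rules cannot all operate. Section 8.2.3 is where the intervention is defined, so anyone setting up delivery would consult it. Followed literally, it puts the app in the hands of future controls at referral, before they consent or are allocated.

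The second gap is smaller. If control links go out at three months by elapsed time, and the 3-month questionnaire is due at the same moment, a control who answers late may have the app before giving the primary outcome.

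Both routes act in the same direction. Section 8.5.1 analyses by intention to treat, so a control who has used Wysa still counts as a control. If the app works, the observed difference shrinks and power falls. Neither the protocol's analysis sections nor the SAP plan to report control use of Wysa, so a null result could not be told apart from control exposure.

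**Working it through.** **Step 1. The link rules side by side**

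| Source | Who | When | How |
|---|---|---|---|
| Protocol 8.2.3 | every referred person | at referral | automatic SMS or email |
| Protocol 6 | patients contacted for consent; no arm named in that sentence | at the consent contact | research assistant |
| Protocol 8.4.1.2 and SAP | intervention arm only | after allocation | automatic email |

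Intent is not in doubt. Section 6 keeps controls on usual service, 8.2.4 names a waitlist comparator, 8.3.3.1 defers control access, and 8.4.1.2 restricts the link to one arm. Section 8.2.3 is the outlier on who receives it. Section 6 differs from 8.4.1.2 on who sends it and when.

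**Step 2. The plan's own sample size**

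Inputs: difference 2 points, SD 6.6, 2:1 usual care to intervention, 80% power (8.3.2.1); two-sided alpha 0.05 (8.5.1).

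With intervention n equal to half of control n, the variance of the difference is 3 × SD² / n(control), so

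n(control) = 3 × SD² × (1.960 + 0.842)² / difference².

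- SD 6.6: 3 × 43.56 × 7.85 / 4 ≈ 256.4, rounded up to 257; with 129 intervention, the total is 386.
- SD 6.66 (the preliminary SD in 8.3.2.1): 262 + 131 = 393, the stated figure.

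The 393 therefore reproduces. The SAP states the 2:1 ratio the other way round; the total at SD 6.6 is then 387, so this check is unaffected.

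**Step 3. Dilution (illustration only)**

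The documents give no contamination rate. Assume a fraction c of controls gain the full 2 points before their PHQ-9. The contrast is then 2 × (1 − c).

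At 262:131, SE = 6.6 × √(1/262 + 1/131) = 0.706, and power ≈ Φ(contrast / SE − 1.960). The last column uses 480 × 0.8 = 384 evaluable participants (256:128).

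| c | Contrast | Power, n = 393 | Power, n = 384 |
|---|---|---|---|
| 0 | 2.0 | 80.8% | 79.9% |
| 5% | 1.9 | 76.7% | 75.8% |
| 10% | 1.8 | 72.2% | 71.2% |
| 20% | 1.6 | 62.0% | 61.0% |
| 30% | 1.4 | 50.9% | 50.0% |

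**Step 4. Short exposure**

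If exposed controls gain only a fraction f of the effect, the contrast is 2 × (1 − c × f). For example, 20% exposed and gaining a quarter of the effect gives c × f = 0.20 × 0.25 = 0.05. That is the 5% row: 76.7% power, not 62.0%. A few days of access would plausibly mean a smaller f still.

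These figures come from an unadjusted comparison. The planned regression adjusts for the stratification variables, including depression severity, so its power would differ.

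**The case against.** The strongest reply is that the documents largely settle who gets the link. Section 8.2.3 reads as a product description, with validation and user-base figures alongside. The assignment rule is in 8.4.1.2, which the protocol's own SPIRIT-AI checklist cites for the allocation mechanism, and the later SAP repeats it. On this view one loose sentence stands against several consistent ones. That is fair as to intent, and it is why the remedy is reconciliation rather than redesign. It does not remove an explicit automatic-send rule from the section that defines the intervention.

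Some stronger readings are tempting but not supported:

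- **That section 6 gives controls the app.** Read whole, it does not: it says controls continue with usual service.
- **That section 6 both contaminates controls and reveals allocation to staff.** These are alternatives. A link handed to everyone reveals nothing about allocation; a link handed to one arm does not reach controls.
- **That control access is fixed by calendar ahead of the PHQ-9.** Only the template GP letter gives an elapsed time. Section 8.3.3.1 speaks of an undefined control period, which could be meant to end at the 3-month assessment. Figure 4 (participant flow), Figure 5 (data collection sequence) and the information sheet are not available and may show the order.
- **That power would fall to about 51%.** This needs 30% of controls to gain the full effect. Neither the rate nor the full gain has a source in the documents, and late responders would have days of access, not three months.

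**Conclusion.** The point holds in two parts. First, 8.2.3 contradicts 8.4.1.2 and the SAP on who receives the link and when, and section 6 differs on who provides it and when. Second, the readable text places control access and the primary PHQ-9 at the same nominal time with neither an order nor a window. The second part is conditional on what Figures 4 and 5 show.

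Contamination is a risk created by the wording, not something the plan intends or that the documents show happened. If it occurred and the app works, the bias would be towards no effect. The power losses in the table are a worst case, resting on an assumed contamination rate, a full 2-point gain in exposed controls, SD 6.6 and an unadjusted comparison. They come closer to realistic if 8.2.3 was followed literally, and are well above what short late access would cost. The correction should be made because it is cheap and protects the primary contrast.

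**What to change.** 1. Reconcile 8.2.3 and section 6 with 8.4.1.2: for trial participants, links come only from the randomisation system, after allocation, and the automatic referral message does not apply to them.
2. Define the control period as ending when the 3-month PHQ-9 is received or at a fixed closing date that applies to both arms, and release control links only then. Align 8.3.3.1 and the GP letter with that definition, and check it against Figures 4 and 5.
3. Add one item on use of Wysa to the control 3-month survey, and record control app-access dates against PHQ-9 completion dates, so that contamination can be reported. App use is already stored automatically (8.4.3.1).
4. The SAP, dated August 2023, describes enrolment in the past tense. If recruitment is complete, state which link rule operated and report those dates.

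Cost: protocol wording, a trigger setting in the email system and one survey item. There are two small downsides. Late-responding controls wait a little longer for access. Release on receipt also gives the control arm alone an incentive to respond, which could make follow-up differ between arms; the common closing date limits this.
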